2. LAY SUMMARY

The aim of this RCT is to evaluate the impact of digital detox on mental health in 18-29 yo students from Austria. Screen time (less than 2 hours per day) as well as social media use (less than 1 hour per day) should be reduced for a period of 3 weeks and the effects should be compared to a controlled group.

A sample of N > 96 should be recruited through newsletter, notices and advertising on social media. The inclusion criteria are more than 3 hours of screen time per day, primarily on social media, and no psychiatric illness for which they are being treated.

After informing and signed the consent form, the participants have to download an App (ESMira®), which processes the whole study. The first step is to fill out sociodemographic data, smartphone usage and mental health questionnaires. After controlling for inclusion and exclusion criteria, ESMira will randomize into intervention (A) and controlled group (B).

The participants in the intervention group (A) should continue their social media use and smartphone screen time unchanged for the first 10 days (Baseline= t1.) After that, the participants should limit their use of social media, such as Instagram, TikTok, Snapchat, Facebook, or similar sites to one hour per day and the complete screen time under two hours per day. To comply with that, participants should use the limiter function of there smartphone or download an additional app. Screen time of the smartphone and the social media use will be tracked automatically or via uploading a screenshot. At the end of the intervention (t2), the mental health questionnaires will be collected again. Afterwards there are no further tasks for the participants in the intervention group (A), social media use is possible again without restrictions, screen time and social media use will be tracked until 3 month follow up (t3). During the study period participants will be asked to additionally wear a fitness tracker to measure daily movement as well as sleep behavior.

The controls group (B) will be asked to continue their social media use and screen time unchanged for 3 month, after that the will be asked to fill out the mental health questionnaires again.

Hypotheses

The primary hypothesis of the study is that mental health, particularly stress, depressive symptoms, and sleep quality will improve after the intervention (t2) compared to the control group as well as compared to baseline.

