3. SYNOPSIS

Trial Title	Smartphone Screentime Reduction improves mental health: A randomized clinical trial				
Internal ref. no. (or short title)	EK GZ 67/2021-2024				
Trial registration	https://osf.io/a9k76				
Sponsor	N.a.				
Funder	N.a.				
Clinical Phase					
Trial Design	Two group, not blinded, randomized controlled trial with a follow up.				

Trial Participants	Healthy adults could participate if thes were 1) between 18 - 29 yo, 2) owning a smartphone and using it at least 3 h/d, and 3) no diagnosed or treated mental disorder, no ongoing psychotherapy or psychopharmaceutic therapy (self-report). Moderately elevated levels in mental health screening questionnaires were no exclusion criteria.			
Sample Size	With a small to medium effect size (Cohens d= 0.45; power .8, significance level < .05, icc = .05), significant results can be expected with a completed data set of minimum 40 people per group. Considering a drop-out rate of 20%, at least 50 people per group were recruited.			
Planned Trial Period	The total study period will be 12 weeks: Screening for eligibility, 10 days baseline phase, 3 weeks intervention, 6 weeks post intervention to follow-up			
Planned Recruitment period	Study protocol submission: August 20, 2023; Approval by Ethical committee October 23, 2023; Information on Social Media and notices at University; Registration November 8, 2023; Screening for Eligibility November 8-10, 2023 Objectives Outcome Measures Timepoint(s)			
Primary	 Depressive Symptoms Well-being Stress Sleep Quality 	 Patient Health Questionnaire (PHQ-9) World Health Organization wellbeing questionnaire (WHO-5) Perceived Stress Questionnaire (PSQ-20) Insomnia Severity Index (ISI) 		
Secondary	 Problematic Smartphone Use Disordered Eating Body Appreciation Anxiety 	 Smartphone Addiction Scale (SAS-SV) SCOFF BAS-2 GAD-7 		
Intervention(s) •	The intervention is reducing smartphone screen time <2/h for 3 weeks. Smartphone screen time will be assessed weekly in both groups using the smartphones' built-in screen time measurements. Weekly, participants will be asked to upload a screenshot from their screen time from the previous week.			

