11. STATISTIC ANALYSIS PLAN

We will use the statistic software IBM SPSS Statistics (IBM Corp., Armonk, NY, USA) to analyze the data. χ^2 -Test and independent samples tests will be used to examine differences at baseline (t0) regarding age, gender, smartphone screen time, physical activity per week, and mental health indicators between the control and the intervention group.

Clinical Trial Protocol Template version 14.0

CONFIDENTIAL

To examine the effect of reduced smartphone screen time on the mental health indicators, repeated measurements ANOVAs (rm-ANOVA) will be applied. The primary hypotheses focuses on the difference between t0 (baseline) and t1 (post-intervention) between control group and intervention group (between group effect). In a secondary analysis, the follow-up time point (t2) will also be included.

Group allocation (control vs. intervention) will be the between-group factor, time will be the within-group factor (t0, t1, t2). Furthermore, a sub-group analysis (rm-ANOVA) will be applied of those, who strictly adhered to the 2h smartphone screen time limit during all three weeks. In case of baseline group-differences in the mental health indicators, these variables will be added as a covariate in the rm-ANOVA. If the sphericity assumption will be violated, the Greenhouse-Geisser correction will be applied. In the post hoc tests, Bonferroni correction will be applied to adjust for multiple comparisons.

Missing values will be estimated with via maximum likelihood estimation.

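### The primary rm-ANOVA contrast is described as a difference in change but labelled a between-group effect, so the test that decides the trial is not fixed

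*Combined protocol and SAP*

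**What the plan says.** Section 11 (Statistic Analysis Plan) plans repeated-measures ANOVAs for the mental health outcomes and states the primary contrast as follows: "The primary hypotheses focuses on the difference between t0 (baseline) and t1 (post-intervention) between control group and intervention group (between group effect". It then sets out the model: "Group allocation (control vs. intervention) will be the between-group factor", with time as the within-group factor. The follow-up time point joins in a secondary analysis. The group-by-time interaction is not mentioned anywhere. Baseline mental health scores enter as covariates only if the groups are found to differ on them at baseline.

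The Synopsis (section 3, Sample Size) gives "Cohens d= 0.45; power .8, significance level < .05, icc = .05" and concludes that "significant results can be expected with a completed data set of minimum 40 people per group". It does not name a power method, define d, state whether the test is one- or two-sided, or explain what the icc refers to.

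The Lay Summary (section 2, Hypotheses) frames the primary hypothesis as improvement "compared to the control group as well as compared to baseline".

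Time labels below follow section 11: t0 is baseline, t1 post-intervention, t2 follow-up.

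**The concern.** In an rm-ANOVA with group between and time within, the between-group effect is the main effect of group. It compares the groups on the average of t0 and t1. Randomisation makes the expected difference at t0 zero, so a treatment difference that exists only at t1 enters that average at half its size. Whether change differs between the groups is tested by group × time, or more efficiently by the t1 difference adjusted for t0.

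The section 11 sentence points to one test by its words and to another by its label. An analyst could defend either. The trial is unblinded and has four main outcomes, so leaving that choice open until the data are in weakens the primary result. If the label were followed literally, a real effect of the planned size would be missed in most such trials.

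**Working it through.** **Inputs.** From the Synopsis: d = 0.45, power .80, significance level .05, icc = .05, 40 completers per group. Assumed here: two-sided testing, equal SDs (set to 1) at t0 and t1, a group difference of 0 at t0 and 0.45 at t1, and a t0–t1 correlation r. The documents give no such correlation. Their only correlation-type figure is the icc of .05, so r is varied from .05 to .9.

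**Step 1: where does 40 per group come from?** A plain two-group comparison needs 2 × (1.960 + 0.842)² / 0.45² ≈ 77.5, so 78 per group. That is not the source. Two rm-ANOVA formulas with two measures, f = 0.45/2 = 0.225 and correlation .05 come close:

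- Between factor: λ = f² × N × 2 / (1 + r) = 0.225² × 80 × 2 / 1.05 = 7.71. Power at 40 per group is .783, and .80 is reached at 42 per group.
- Within-between interaction: λ = f² × N × 2 / (1 − r) = 0.225² × 80 × 2 / 0.95 = 8.53. Power at 40 per group is .822, and .80 is reached at 38 per group.

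Both lie within two participants of the stated figure, so it does not identify the intended test.

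Neither formula matches a randomised trial with no expected baseline difference. The first assumes a group difference of 0.45 averaged over t0 and t1. The second, with f = 0.225, implies cell deviations of ±0.225, so the group difference moves from −0.45 to +0.45. That is a difference in change of 0.90 SD: 0.90² × 20 / (2 × 0.95) = 8.53, the same λ.

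**Step 2: power of each candidate test.** The noncentrality is (effect / SD) × √(n/2), with n = 40 and √20 = 4.472:

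- Group main effect: effect 0.225, variance (1 + r)/2.
- Group × time: effect 0.45, variance 2(1 − r).
- t1 adjusted for t0 (ANCOVA): effect 0.45, variance 1 − r².

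At r = .5 this gives:

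- Main effect: 0.225/0.866 × 4.472 = 1.16, power 21%.
- Group × time: 0.45/1.000 × 4.472 = 2.01, power 51%.
- ANCOVA: 0.45/0.866 × 4.472 = 2.32, power 63%.

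| r | Group main effect | Group × time | ANCOVA |
|---|---|---|---|
| .05 | 28% | 30% | 51% |
| .3 | 23% | 39% | 55% |
| .5 | 21% | 51% | 63% |
| .7 | 19% | 73% | about 80% |
| .9 | 18% | 99% | 99.5% |

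Simulation agrees at r = .05 (main effect 28.0%, interaction 30.2%) and at r = .5 (20.7% and 50.9%).

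**Step 3: the conditional covariate rule.** If an outcome's t0 score is entered as a covariate while t0 is also a repeated measure, the adjusted group effect on the t0/t1 average is exactly half the adjusted t1 difference, with half its standard error. It is then the same test as ANCOVA at t1. Without the covariate it is the unadjusted average. What the labelled effect tests would therefore depend on a preliminary baseline test.

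**The case against.** The strongest reply is that the sentence, read as a whole, describes a t0-to-t1 difference compared between groups. That is group × time, a valid test of the stated question. On this view the bracketed label only separates the controlled comparison from within-group change. This stands as a fair reading, and perhaps the more natural one. A reader might infer that the plan has chosen the main effect and that the trial therefore has about 21% power. The documents do not support that flat statement: the choice is unclear, and 21% needs both the main-effect reading and an assumed correlation of .5.

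A reader might also take 40 per group as evidence that a between-factor test was intended. It is not. The interaction formula fits equally well, and at 40 per group it is the one that meets the stated .80.

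On the Lay Summary, improvement over control and improvement over baseline are joined, with control named first. Within-group change alone would not meet the hypothesis as written, so it cannot be said that the plan counts uncontrolled change as success. What remains is that the second half is an uncontrolled comparison, absent from the primary contrast in section 11.

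Finally, preferring ANCOVA to group × time is a matter of efficiency, not validity. That is correct, and group × time is accepted below as the minimum. None of this removes the need to name the test, because two defensible readings lead to different F-tests.

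**Conclusion.** The concern holds as an ambiguity with a conditional cost. The label and the words of the primary contrast point to different tests, and the interaction is never named. If the group main effect were used, power at 40 completers per group would be about 18–28% over correlations from .9 down to .05. That is below group × time and baseline-adjusted ANCOVA at every correlation examined, and far below the stated 80%. These figures assume that d = 0.45 is the t1 difference, that the groups do not differ at t0, that SDs are equal and that testing is two-sided at .05.

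It would be wrong to infer that the label accounts for the whole shortfall from 80%. On the same assumptions group × time reaches 80% only at a correlation of roughly .75, and ANCOVA at roughly .7. Naming the right test removes the worst case and the freedom to choose, but does not by itself deliver the stated power.

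**What to change.** In section 11, state the primary test for each main outcome as the group difference at post-intervention, adjusted in all cases for the same outcome's baseline score. An ANCOVA or the t1 contrast of a mixed model would do this. It replaces the rule that adds baseline only when the groups differ on it. If rm-ANOVA is kept, the minimum is to name the group × time term over baseline and post-intervention. In either case, state that the group main effect is not used to judge the primary hypothesis.

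In section 2, limit the primary hypothesis to the comparison with control. Change from baseline within the intervention group can be reported descriptively.

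The cost is a few sentences. Baseline scores are already collected, so no new data are needed. The Synopsis should then say which test, which definition of d and which correlation the 40 per group refers to.

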More and more studies are highlighting the high addictive potential of social media (Sun et al., 2021). This seems to be present with most social media platforms, with TikTok (and presumably other short video formats) appearing to have particularly high addictive potential (Marengo et al., 2022).

This is consistent with earlier findings that reported a significant increase in boredom or craving (a term from addiction medicine describing intense desire for the addictive substance during withdrawal) when completely abstaining from social media for a week (Stieger et al., 2018). This study also showed that after just one week, there was no lasting change in usage behavior. After the intervention, participants resumed using social media as frequently as before (Stieger et al., 2018).

The reasons and causes for the intensive use of social media are certainly not fully understood. Activation of the brain's reward system through likes and positive interactions or the fear of missing out ("Fear of Missing Out" or FOMO) may repeatedly lead us to reach for our smartphones. But self-presentation, recognition, or "social comparison" can also play a role.

While social media can have advantages for entertainment, distraction, or contact with others, excessive use can lead to a range of negative consequences. In response, the term "Digital Detox" has emerged to emphasize the need for a conscious reduction in digital use.

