11.1. Sample Size Determination

According to the power analysis 40 per group should finish the study per group, in case of 20% drop outs, a minimum of 96 participants should be included.

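### Follow-up is analysed only by adding t2 to a three-level rm-ANOVA; its omnibus F does not separate a lasting effect from a vanished one, and no follow-up contrast is specified

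*Combined protocol and SAP*

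**What the plan says.** Section 11 (Statistic Analysis Plan) sets the primary comparison as the group difference between t0 (baseline) and t1 (post-intervention). On follow-up it says "In a secondary analysis, the follow-up time point (t2) will also be included". Group is the between factor and time the within factor, with levels t0, t1 and t2. Greenhouse-Geisser is applied if sphericity fails, and post hoc tests are Bonferroni-corrected. The section does not say which pairs those tests compare, or whether they run between groups or within a group over time. It names no group comparison at t2, no t0-to-t2 contrast and no criterion for a lasting effect.

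Section 5 schedules all four main outcomes (PHQ-9, WHO-5, PSQ-20, ISI) at follow-up, and Section 9 lifts the restrictions after the intervention. The hypothesis in Section 2 concerns the end of the intervention only. Section 4 reports of an earlier one-week abstinence study: "After the intervention, participants resumed using social media as frequently as before".

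Time labels differ between sections: Sections 2 and 9 call follow-up t3, and Section 11 calls it t2. This note uses the Section 11 labels.

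**The concern.** A follow-up visit after unrestricted use resumes naturally raises the question whether any benefit is still there. The only test that Section 11 identifies for that visit is the three-level group-by-time F, which has 2 numerator degrees of freedom and reacts to any difference in pattern over the three visits. An effect at t1 that is gone by t2 can make it significant just as an effect that stays can.

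If a significant F from the model that includes follow-up were taken as evidence of durability, the claim could rest entirely on the post-intervention visit. Leaving the post hoc comparisons open also means that the comparison which would settle the matter can be chosen after the data are seen, in an unblinded trial with four main outcomes.

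**Working it through.** **Inputs from the documents (Section 3, Synopsis).** "Cohens d= 0.45; power .8, significance level < .05, icc = .05", and a "completed data set of minimum 40 people per group".

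**Assumed.** Two-sided tests; d = 0.45 in SD units at each visit where an effect exists; 40 per group with follow-up data; within-person correlation rho of .05, .5 and .7. The role of the stated icc is not explained, so .05 is one end of the range. The higher values are not from the documents.

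**1. The plan's own figure.** A between-group test on the mean of two measurements with correlation .05 has variance (1 + .05)/2 = .525. Then n = 2 × (1.96 + 0.84)² × .525 / 0.45² ≈ 41 per group. Non-central F versions for two measurements give 42 (between effect) and 38 (interaction). The stated 40 is therefore reproduced approximately, as a two-measurement calculation. It does not size a follow-up contrast.

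**2. Omnibus F, equal correlations.** Write the group differences at (t0, t1, t2) as a pattern. The sum of squares about the pattern's own mean is:
- vanished (0, d, 0): (1/9 + 4/9 + 1/9)d² = 2d²/3
- lasting (0, d, d): (4/9 + 1/9 + 1/9)d² = 2d²/3

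Non-centrality is λ = (n/2) × SS / (1 − rho) = 20 × (2/3 × 0.2025) / (1 − rho) = 2.7 / (1 − rho), with 2 and 156 df.

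| rho | λ | Power, lasting | Power, vanished |
|---|---|---|---|
| .05 | 2.84 | 30.1% | 30.1% |
| .5 | 5.40 | 52.8% | 52.8% |
| .7 | 9.00 | 76.2% | 76.2% |

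Simulation with the Greenhouse-Geisser correction agrees to within about one point.

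**3. When the conditions are relaxed.** Under AR(1) correlations with Greenhouse-Geisser (20,000 runs), the F is significant in 44% (lasting) versus 46% (vanished) at rho .5, and 62% versus 69% at rho .7. For a half-kept effect (0, d, d/2), SS = d²/2, so at rho .5 λ = 4.05 and power is 41%, against 53% for a vanished effect.

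**4. Favourable reading of the post hoc step.** Compare the groups at t2 with a two-sample test, non-centrality 0.45 / √(2/40) = 2.01. Uncorrected, it is significant in about 51% of trials if the effect lasts and 5% if it has gone. With Bonferroni for three comparisons, power is about 34%. Requiring a significant omnibus F first, the lasting effect is detected in about 16, 23 and 28% of trials (rho .05, .5, .7), and a vanished one is flagged in about 1%.

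**5. Baseline-adjusted contrast at t2.** The standard error is √(2(1 − rho²)/40).

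| rho (t0 with t2) | Non-centrality | Power if lasting | Rejection if vanished |
|---|---|---|---|
| .05 | 2.01 | 51% | about 5% |
| .5 | 2.32 | 63% | about 5% |
| .7 | 2.82 | 79.5% | about 5% |

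The correlation that matters is t0 with t2. AR(1) at .7 gives .7² = .49, so the .5 row applies. If Bonferroni were applied across four outcomes (.05/4 = .0125, critical t about 2.56), power falls to about 30, 40 and 60%.

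**6. Unadjusted alternative.** The between-group contrast on t0-to-t2 change gives 31, 52 and 73% if the effect lasts and about 5% if it has gone.

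**The case against.** The strongest reply is that the omnibus F is not the plan's only step. Section 11 also provides corrected post hoc tests. In a randomised trial, a plain comparison of the two groups at t2 is a valid test of whether they differ there, baseline-adjusted or not. Step 4 shows that it does separate the two cases. This stands. A reader might infer that the plan cannot show persistence at all; the documents do not support that, because such a test is neither prespecified nor excluded. What remains is that nothing commits the investigators to it, that within-group comparisons over time would meet the same wording, and that even the favourable version has low power.

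Three further points also stand:
- Equal power for the lasting and vanished patterns is exact only under equal correlations and full or zero retention. The AR(1) departures run against the plan, but the condition has to be stated.
- No persistence hypothesis is written anywhere. The question is inferred from the follow-up visit.
- The study described in Section 4 tested one week of complete abstinence and, as quoted, reports usage rather than symptoms. It makes fade-out a plausible scenario to plan for; it does not establish that symptoms will return.

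Baseline adjustment is not the only valid choice, since the change contrast also separates the cases. It is preferred here because it is at least as powerful across the assumed range.

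**Conclusion.** The point holds in limited form. The three-level group-by-time F does not by itself tell a lasting effect from a vanished one, and Section 11 specifies no comparison that would. Under the stated assumptions, the F is significant in about 30 to 76% of trials in either case. A reader might take those percentages as rates of false claims of durability. They are not: they become so only if the F alone is taken as the evidence and the post hoc step and the t2 means are ignored.

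The cost of leaving the plan as it is can be seen in the detection of a lasting effect: about 16 to 28% on the favourable reading, against about 51 to 80% for a single baseline-adjusted contrast before any correction across outcomes. These ranges rest on d = 0.45 at t2, 40 per group with follow-up data, and assumed correlations. The qualitative conclusion does not depend on the correlation chosen. The analysis is secondary and the primary t0-to-t1 comparison is unaffected, so this should be corrected but does not threaten the main result.

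**What to change.** In Section 11, replace the sentence on follow-up with wording to this effect: for each main outcome, the follow-up question is tested by one contrast, the group difference at t2 adjusted for the t0 score, reported with its 95% confidence interval; any statement about a lasting effect rests on this contrast; the three-level group-by-time F is descriptive. Keep the t0-to-t1 primary comparison in its own model.

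Also state whether a multiplicity correction applies to this contrast across the four main outcomes (if so, the power figures are lower, as in step 5), and list any post hoc comparisons that remain, saying whether each is between or within groups.

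The cost is a few sentences, ideally fixed before outcome data are examined. No new data, visits or participants are needed.

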7.2. Exclusion Criteria

The participant may not enter the trial if ANY of the following apply:

- Diagnosed mental disorder
- Ongoing psychotherapy.
- Psychotropic drugs.
- Screen time daily less than 3 hours.

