9. TRIAL INTERVENTIONS

Screen time (less than 2 hours per day) as well as social media use (less than 1 hour per day) should be reduced for a period of 3 weeks and the effects should be compared to a controlled group. A sample of N > 96 should be recruited through newsletter, notices and advertising on social media. The inclusion criteria are more than 3 hours of screen time per day, and no psychiatric illness for which they are being treated. After informing and signed the consent form, the participants have to download an App (ESMira®), which processes the whole study. The first step is to fill out sociodemographic data, smartphone usage and mental health questionnaires. After controlling for inclusion and exclusion criteria, ESMira will randomize into intervention (A) and controlled group (B). The participants in the intervention group (A) should continue their social media use and smartphone screen time unchanged for the first 10 days (Baseline.) After that (t1), the participants should limit their use of social media, such as Instagram, TikTok, Snapchat, Facebook, or similar sites to one hour per day and the complete screen time under two hours per day. To comply with that, participants should use the limiter function of there smartphone or download an additional app. Screen time of the smartphone and the social media use will be tracked automatically or via uploading a screenshot. At the end of the intervention (t2), the mental health questionnaires will be collected again. Afterwards there are no further tasks for the participants in the intervention group (A), screen time and social media use is possible again without restrictions. Screen time and social media use will be tracked until 3 month follow up (t3). During the study period participants will be asked to additionally wear a fitness tracker to measure daily movement as well as sleep behavior. The controls group (B) will be asked to continue their social media use and screen time unchanged to follow-up, after that the will be asked to fill out the mental health questionnaires again. After follow up, control group (B) will be offered to participate at intervention to keep drop outs and missing values low.

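### The strict-adherer rm-ANOVA is selected on behaviour after randomisation and carries no caveat, so it can show a benefit where the intervention has none.

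*Combined protocol and SAP*

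**What the plan says.** After the main rm-ANOVAs, section 11 adds a "sub-group analysis (rm-ANOVA) will be applied of those, who strictly adhered to the 2h smartphone screen time limit during all three weeks". For the rm-ANOVAs in general it states that "Group allocation (control vs. intervention) will be the between-group factor". It gives no separate comparator for the sub-group.

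The limit belongs to the intervention group only. Section 9 asks controls to "continue their social media use and screen time unchanged to follow-up", and section 7.2 excludes people with "Screen time daily less than 3 hours".

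The synopsis says that "Smartphone screen time will be assessed weekly in both groups" and that "participants will be asked to upload a screenshot from their screen time from the previous week". The only planned adjustment is conditional: "In case of baseline group-differences in the mental health indicators, these variables will be added as a covariate in the rm-ANOVA". Nothing in the plan calls the adherer analysis exploratory or limits how it may be interpreted.

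Time points below follow section 11: t0 is baseline and t1 is post-intervention.

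**The concern.** Randomisation makes the two groups comparable as allocated. It does not make the part of one group that kept a rule for three weeks comparable with the whole of the other group.

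The documents themselves make selection plausible. Section 10 warns of discomfort, unrest and withdrawal symptoms during the intervention, and stress and sleep are main outcomes. Someone who feels worse may break the limit and so leave the sub-group. Someone whose term is getting easier may keep the limit without effort and would have improved anyway.

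What is at stake is the interpretation. A larger difference among adherers is readily taken to mean that the intervention works when it is followed, yet selection can produce the same pattern with no effect at all.

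**Working it through.** **1. Group size used.** The synopsis gives "Cohens d= 0.45; power .8, significance level < .05, icc = .05" and 40 completers per group. Averaging two time points, with two-sided 5% assumed because sidedness is not stated: n = 2 × (1.960 + 0.842)² / 0.45² × (1 + 0.05)/2 = 77.5 × 0.525 = 40.7, so 41. The stated 40 is reproduced to within one participant (power at 40 is 0.793). I use 40 per group below.

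**2. Is there a matching control sub-group?** Controls enter at 3 h/day or more and are asked not to change. A control who follows that instruction cannot fall under a 2 h rule. Two readings remain:
- Adherers against all controls. This fits the stated between-group factor.
- Change over time within adherers only. This has no control, so it cannot separate the intervention from time, season or regression to the mean.

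**3. Size under the first reading, true effect zero.** With two time points, the group-by-time test of the rm-ANOVA is the two-sample t-test on change scores. Let p be the share of the intervention group that adheres, c the standard normal cut-off with upper tail p, φ the standard normal density, and r the correlation of a normal adherence propensity with the change that would occur without any effect (positive means improvement). Then

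spurious difference = r × φ(c) / p, in SDs of change.

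- p = 0.50: φ(c)/p = 0.3989/0.50 = 0.798
- p = 0.30: φ(c)/p = 0.3477/0.30 = 1.159

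The documents give neither p nor r, so both are assumptions. Rejection rates come from 100,000 simulated trials per setting, adherers against 40 controls, two-sided 5%.

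| Share p | r | Spurious difference (SD of change) | Rejection |
|---|---|---|---|
| 0.50 | 0.1 | 0.080 | 5.9% |
| 0.50 | 0.2 | 0.160 | 8.8% |
| 0.50 | 0.3 | 0.239 | 14.1% |
| 0.30 | 0.1 | 0.116 | 6.4% |
| 0.30 | 0.2 | 0.232 | 10.2% |
| 0.30 | 0.3 | 0.348 | 17.6% |

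**4. Where the bias vanishes or reverses.**
- r = 0: no bias, rejection 5.0 to 5.1%.
- r = −0.3: differences of −0.239 and −0.348 SD, with rejection of 13.7% and 17.5%, almost all of it against the intervention.
- Adherence correlated equally (0.1 to 0.3) with t0 and t1, with a t0–t1 correlation of 0.6 assumed: difference 0.00 SD, rejection 4.9 to 5.0%. The change score cancels a stable difference. This holds for the unadjusted group-by-time test. A test of the group main effect would still be biased.

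**5. Reference.** In a separate run of 20,000 trials per setting (p from 0.25 to 0.75, r from 0 to 0.5), comparing all 40 per group as allocated kept rejection at 4.5 to 5.3%.

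**The case against.** The strongest reply has four parts.

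- **The comparator is inferred.** Section 11 never says that adherers are compared with all controls. This stands, and the point is therefore worded for both readings. Neither gives a randomised estimate.
- **The bias is conditional.** Stable motivation or a stable stress level, related equally to both scores, does not bias the unadjusted group-by-time test. This also stands. A reader might infer that the analysis must favour the intervention, or that its false-positive rate is certainly inflated. The documents do not support that: they give no adherence rate and nothing on how adherence relates to untreated change. At r = 0.1 the inflation is slight.
- **Units.** It is tempting to express the bias as a percentage of the assumed d of 0.45. The bias is in SDs of change. One such SD equals √(2(1 − ρ)) raw-score SDs, where ρ is the t0–t1 correlation: 0.77 at ρ = 0.7, 1.00 at 0.5 and 1.38 at 0.05. The plan does not settle which SD its d uses, so no percentage is given here.
- **It is an added analysis.** The primary hypothesis rests on control against intervention, and neither the sample size nor the primary result depends on the sub-group. This stands and limits the consequence. It does not supply the missing caveat.

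The conditional covariate is not an answer. It is entered only if baseline mental health scores differ, and it cannot capture selection on the course still to come. Maximum likelihood for missing values and the Bonferroni correction do not address selection into adherence either.

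**Conclusion.** The point holds in a conditional form. The adherer rm-ANOVA is not protected by randomisation under either reading of its comparator, and the plan attaches no warning. It can show a benefit without any effect if adherence is related to the change that would have occurred anyway.

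The table in the working gives the size for correlations of 0.1 to 0.3. The result rests on assumed adherence shares of 30% and 50%, a normal adherence propensity, 40 per group and all controls as comparator. The sign of the correlation is also unknown.

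A reader might go further and conclude that the trial's main result is compromised. It is not: the comparison of the groups as allocated does not use the sub-group. The change should be made, but it concerns a secondary claim.

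**What to change.** In section 11, state that the strict-adherer analysis is descriptive and non-causal, report it without a p-value against controls, and base every claim of effect on all randomised participants as allocated. Say also how strict adherence is judged from the weekly screenshots and how a missing screenshot is handled, so that the description can be reproduced.

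Optional: add a supportive instrumental-variable (complier-average) estimate with allocation as instrument and t0 adjustment, using the weekly screen time already collected in both groups. It must state its assumption that allocation acts only through screen time. That is doubtful here, because there is no blinding, the outcomes are self-reported and the intervention also limits social media separately. It is therefore a choice for the investigators and not a required replacement.

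The cost is a few sentences, plus one model if the option is taken. The adherer result can then no longer be cited as evidence of effect. The instrumental estimate would have a wider interval and rest on an assumption that the data cannot test.
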